2.2 Rationale

In recent years, the ability to more precisely target and treat disease with RT has sparked interest in delivering larger fraction sizes (e.g., > 8 Gy/fraction), thereby reducing treatment time, and perhaps improving biologic effect. For other sites such as the lung and liver, this form of therapy (known as Stereotactic Body Radiation Therapy) has achieved high rates of local control, with no appreciable increase in toxicity of treatment with limited follow-up (Timmerman, 2007; Kavanagh, 2006). In

the setting of unresectable pancreatic cancer, there are two published experiences using SBRT techniques (Hoyer, 2005; Koong, 2004). The experience from Stanford (Koong, 2004) with 15-25 Gy in one fraction has been favorable, with only 5 of 15 patients treated on this dose escalation protocol demonstrating grade 1-2 toxicity (nausea, diarrhea, abdominal pain) with no patient demonstrating grade 3+ toxicity on initial report. Meanwhile, all 6 patients treated to the highest dose of 25 Gy had local control of the disease. Longer term follow-up of 77 patients treated with 25 Gy demonstrated a local control rate of 84% at 1 year, with moderate late toxicity (Grade 2+) in 10 (13%) of patients (Chang, 2008). The nature of the toxicity was related to gastrointestinal function, including ulceration of the small bowel (n=3) or stomach (n=3), stricture of the duodenum (n=1) or biliary system (n=2), or perforation of the small bowel (n=1). Toxicity was increased for men who received prior external beam radiation therapy in addition to the single stereotactic dose of 25 Gy. The risk of severe toxicity (G3+) was approximately 10% in patients treated with SBRT alone. In contrast, a phase II study from Denmark (Hoyer, 2005) treated 22 patients with 45 Gy (15 Gy x 3 fractions) for unresectable pancreatic cancer and found lower rates of control. Local control was only 57% at 6 months. This lower rate of local control is consistent with the approximately 50% rates observed in other studies giving standard fractionation RT, including post-operative (Smeenk, 2007) and definitive settings (Moertel, 1981). Meanwhile, grade 2+ toxicity (defined in this study as performance status, nausea, diarrhea, or pain at day 14 assessment) was 79%. Of note, pretreatment evaluation revealed that patients had symptoms consistent with grade 2+ toxicity in approximately 63%, so the actual increase in toxicity over baseline is difficult to quantify given the grading schema used and the lack of follow-up past day 14. These discrepant reports of SBRT indicate a need for further trials to help identify the role of SBRT for unresectable pancreatic cancer. With the poor ability to achieve local control, it is of interest to note whether SBRT could be more effective than standard fractionation. Furthermore, as neither of these studies followed detailed gastrointestinal toxicity according to prospectively defined dosimetric planning criteria, it is important to better characterize the nature and frequency of such treatment.

From a practical standpoint, if there existed an effective and safe means to achieve local control and contract the length of RT into two weeks, patients would be more likely to tolerate aggressive systemic therapy. A recent phase III study randomizing patients with unresectable pancreatic cancer to gemcitabine chemotherapy with or without sandwich 5-FU, cisplatin, and concurrent RT found that the aggressive local therapy was associated with significant toxicity, which limited administration of systemic therapy and negatively impacted survival (Mornex, 2007). Meanwhile, “standard” administration of 5-FU with continuous course RT is also associated with a risk of severe toxicity. The RTOG 97-04 demonstrated a 59% risk of any Grade 3 non-hematologic toxicity in patients who received 5-FU/RT and adjuvant systemic therapy after pancreaticoduodenectomy (Regine, 2008). The hypothesis of any SBRT approach for locally advanced, non-metastatic pancreatic cancer is that this combination of dose-intense local therapy over 2 weeks will be relatively well tolerated, and not preclude further aggressive systemic therapy. It is possible that the proposed treatment will result in less quality of life decline than standard fractionation. Meanwhile, with a positive initial experience in the unresectable setting, SBRT could be studied in the preoperative setting (e.g., for borderline resectable patients). RT with

standard fractionation has been studied in the preoperative setting, with disappointing results. It is estimated that, after careful selection of borderline resectable patients and treatment with preoperative radiation therapy and chemotherapy, approximately 40% of these patients are able to then undergo resection (Katz, 2008). Resectability is the most important prognostic factor for success after treatment, and as such, is an important potential endpoint to evaluate.

3. PATIENT SELECTION

3.1 Eligibility Criteria

- 3.1.1 Patients must have histologically confirmed, unresected cancer of the pancreas or ampulla. The cancer may include any invasive histology (e.g. adenocarcinoma, neuroendocrine carcinoma). Patients with lymph node involvement or distant metastasis may be included if it is felt that local control of the primary site of disease would help reduce, or prevent the development of, local symptoms.
- 3.1.2 Patients must have measurable radiographic disease. Patients with previous complete resection are only eligible if there is measurable radiographic disease which is clearly felt to represent locally recurrent disease.
- 3.1.3 Patients may receive any number of cycles of chemotherapy prior to treatment with SBRT, but not within 2 weeks of the first fraction of RT. Patients are not required to receive any chemotherapy to be eligible for study enrollment.
- 3.1.4 Age ≥ 18 years. The effects of this therapy are unstudied in the pediatric population.
- 3.1.5 ECOG performance status ≤ 2 (Karnofsky $\geq 60\%$, see Appendix A).
- 3.1.6 Life expectancy of greater than 3 months.
- 3.1.7 Patients must have normal organ and marrow function as defined below:
 - Absolute neutrophil count (ANC) $\geq 1,800$ cells/mm³
 - Platelets $\geq 100,000$ cells/mm³
 - Hemoglobin ≥ 8.0 g/dl
 - Creatinine $\leq 2 \times$ institutional upper limit of normal
 - total bilirubin $\leq 2.5 \times$ institutional upper limit of normal
 - AST(SGOT) or ALT(SGPT) $\leq 2.5 \times$ institutional upper limit of normal
- 3.1.8 Ability to understand and the willingness to sign a written informed consent document.

3.2 Exclusion Criteria

- 3.2.1 3.2.2 Concurrent investigational therapy delivered over the period of treatment or observation (28 days post-RT) for dose limiting toxicity.
- 3.2.3 Prior radiation therapy to the abdominal area which would overlap with the proposed area of treatment.
- 3.2.4 Pregnancy. Radiation therapy is known to have adverse effects on the fetus.
- 3.2.5 Primary disease >7.5 cm in largest diameter as measured by CT or MRI.
- 3.2.6 Gross extension of tumor into the lumen of the duodenum.
- 3.2.7 Uncontrolled intercurrent illness including, but not limited to ongoing or active infection, symptomatic congestive heart failure, unstable angina pectoris, cardiac arrhythmia, or psychiatric illness/social situations that would limit compliance with study requirements.
- 3.2.8 Use of bevacizumab or vascular endothelial growth factor inhibitor chemotherapy within 3 months before RT or 6 months after RT.

3.3 Inclusion of Women and Minorities

Both men and women and members of all races and ethnic groups are eligible for this trial.

4. TREATMENT PLAN

4.1 Radiation Therapy Dose Escalation

Treatment will be administered on an outpatient basis. Details regarding planning and administration of RT are described in Section 6. Reported adverse events and potential risks are described in Section 7.

Dose-Escalation Schedule	
Dose Level	
Level -1	7.5 Gy x 3
Level 1	10 Gy x 3
Level 2	12.5 Gy x 3
Level 3	15 Gy x 3

4.2 Measuring Health Related Quality of Life

Patient reported outcome measures will include the Functional Assessment of Cancer Therapy–Hepatobiliary (FACT-Hep) questionnaire, a 45-item self-reported instrument designed to measure health-related quality of life (HRQOL) in patients with hepatobiliary cancers including pancreatic cancers. The FACT-Hep consists of the 27-item FACT-G, which assesses generic HRQOL concerns including physical, emotional, social and functional well being, and the newly validated 18-item Hepatobiliary Subscale (HS), which assesses disease-specific issues (see Appendix D). The questionnaire will be administered to all patients on trial at baseline, post treatment at follow up exams at 1,2,4,6,9 and 12 months from the start of SBRT. The questionnaire will be completed in writing by the patients, and after 12 months from the start of radiation therapy it will not be required.

4.3 Definition of Dose-Limiting Toxicity

The evaluation period of acute toxicity will be defined by the period of 28 days following the first fraction of RT. Dose Limiting Toxicity (DLT) will be defined according to Common Toxicity Criteria version 3.0 (See Appendix B) and includes the following acute toxicities:

- Grade 4 nausea (life-threatening consequences)
- Grade 4 skin toxicity (necrosis or ulceration of full thickness dermis, spontaneous bleeding from involved site)
- Grade 3+ liver toxicity including symptomatic ascites requiring invasive procedure, or total bilirubin $>3 \times$ ULN, or AST $>5 \times$ ULN, or ALT $>5 \times$ ULN that persists until day 28, and is attributable to radiation therapy.
- Grade 3+ enteritis (abdominal pain, fever, change in bowel habits with ileus, peritoneal signs) that is attributable to radiation therapy.

Patients must have a minimum of 3 weeks of follow-up after RT start for patient data to contribute enough follow-up for consideration of dose-limiting toxicity. However, any DLT that occurs with shorter follow-up will count towards the dose escalation rules. In addition, any grade 5 toxicity (i.e., death) considered possibly, probably or likely related to RT will be considered a DLT.

Any late toxicity that occurs beyond the 4 week period of evaluation will be closely followed and documented as a toxicity of interest. Included are the following severe late toxicities of RT:

- Grade 3+ gastrointestinal ulcer, fistula, stricture, or perforation (symptomatic and severely altered GI function, IV fluids or TPN ≥ 24 hrs, intervention indicated)
- Grade 3+ gastrointestinal mucositis (confluent ulcerations or pseudomembranes, bleeding with minor trauma)
- Grade 3+ gastrointestinal bleed (transfusion, interventional radiology or endoscopic or operative intervention)
- Grade 3+ gastrointestinal necrosis (inability to aliment adequately by GI tract, interventional radiology, intervention indicated)
- Grade 3+ liver toxicity including symptomatic ascites requiring invasive procedure, or total bilirubin $>3 \times$ ULN, or AST $>5 \times$ ULN, or ALT $>5 \times$ ULN, or asterixis, that is attributable to radiation therapy.

- Grade 3+ enteritis (abdominal pain, fever, change in bowel habits with ileus, peritoneal signs) that is attributable to radiation therapy.
- Grade 3+ pancreatitis (interventional radiology or operative intervention indicated)
- Grade 3+ cholecystitis (interventional radiology or operative intervention indicated)

These severe, late toxicities will be evaluated between 1 and 12 months of therapy. There is no minimum follow-up time after RT start required for patient data to contribute enough follow-up for toxicities of interest.

Enrollment of 12 additional toxicity-evaluable patients at the MTD will provide a cohort of 18 patients at the putative MTD. If six or fewer of the 18 patients experience a toxicity of interest during the evaluation period, the combination will be considered tolerable. If 7 or more patients experience a toxicity of interest, the study committee will suspend accrual and determine whether further dose modifications are needed; the protocol will be amended accordingly. If the true probability of DLT at the MTD is 50%, the combination will be identified as too toxic with probability 0.88. If the true probability of DLT at the MTD is 25%, the combination will be identified as having an acceptable toxicity profile with probability 0.86.

Management associated with the above adverse events is outlined in Section 7.

Dose escalation will proceed within each cohort according to the following scheme. Dose-limiting toxicity (DLT) is defined above.

Number of Patients with DLT at a Given Dose Level	Escalation Decision Rule
0 out of 3	Enter 3 patients at the next dose level
≥ 2	Dose escalation will be stopped. This dose level will be declared the maximally administered dose (highest dose administered). Three (3) additional patients will be entered at the next lowest dose level if only 3 patients were treated previously at that dose.
1 out of 3	Enter at least 3 more patients at this dose level. 
 • If 0 of these 3 patients experience DLT, proceed to the next dose level. • If 1 or more of this group suffer DLT, then dose escalation is stopped, and this dose is declared the maximally administered dose. Three (3) additional patients will be entered at the next lowest dose level if only 3 patients were treated previously at that dose.
≤ 1 out of 6 at highest dose level below the maximally administered dose	This is generally the recommended phase 2 dose. At least 6 patients must be entered at the recommended phase 2 dose.

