4.5 Duration of Therapy

Duration of SBRT is to occur within a 10 day time period. Completion of the three fractions of RT will be delayed or foregone if:

- Intercurrent illness that prevents further administration of treatment,
- Further treatment is felt to be likely to result in severe and permanent impairment, or death (life-threatening toxicity),
- The patient decides to withdraw from the study, or
- General or specific changes in the patient's condition render the patient unacceptable for further treatment in the judgment of the investigator.

The use of chemotherapy after RT will be at the discretion of the treating physician.

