5.2 RT Planning Parameters

- 5.2.1. The definition of volumes will be in accordance with the ICRU Report 62: Prescribing, Recording and Reporting Photon Beam Therapy. (ICRU, 1999)
- 5.2.1.1. A gross tumor volume (GTV) will be entered for each lesion, based on available imaging data.
- 5.2.1.2. In the absence of respiratory gating, an internal target volume (ITV) will be defined as the volume that accounts for intrafraction target motion.
- 5.2.1.3. A clinical target volume (CTV) will be defined as the GTV or ITV (when available) plus a margin for microscopic extension.
- 5.2.1.4. A planning target volume (PTV) will be determined which will correspond to CTV plus appropriate margin for tumor motion and set-up uncertainty.
- 5.2.2. 3D coplanar or non-coplanar beam arrangements will be custom designed for each case to deliver highly conformal prescription dose distributions. The treatment plan used for each patient will be based on an analysis of the volumetric dose, including dose volume histogram of the PTV and normal structures. 3D “forward” planning or “inverse” planning with beamlet intensity modulated treatment planning are allowed.
- 5.2.3. Treatment is to be delivered using a linear accelerator and photon energies ≥ 6 MV.
- 5.2.4. Corrections will be made to account for tissue heterogeneity.
- 5.2.5. RT is to be delivered to each site in 3 fractions over a period of up to 10 total days.
- 5.2.6. RT Dose: A phase I escalation of doses will be performed in order to determine in MTD in Gy. Doses of radiation will start at Level 1 and increase as follows in order to determine the MTD in Gy:
 - Level 1: 10 Gy/ fraction \times 3 fractions = 30 Gy

Level 2: 12.5 Gy/fraction x 3 fractions = 37.5 Gy

Level 3: 15 Gy/fraction x 3 fractions = 45 Gy

If DLT is met at Level 1, dose will be de-escalated to Level -1: 7.5 Gy x 3 fractions = 22.5 Gy

5.2.7. Doses will be prescribed to the PTV. The PTV may be covered by a lower isodose line than usually used in conventional radiotherapy planning, typically around 80% but ranging from 60-100%. Ideally, the prescription dose will cover >90% of the GTV (V100 GTV > 90%, and V95PTV > 90%). A lower coverage goal (with no minimum requirement of PTV coverage) will be acceptable if necessary to meet normal tissue constraints, which will be assigned priority over tumor coverage.

5.2.7.1. Any dose > 110% must be within the PTV.

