6. ADVERSE EVENTS

Adverse event (AE) monitoring and reporting will be performed.

- Radiation side effects are limited to the area involved in the treatment field. Acute and late toxicity related to radiation therapy may include fatigue, nausea and vomiting, skin erythema, subcutaneous fibrosis, esophagitis, pericarditis, diarrhea, myelitis, damage to the small bowel (including stricture or obstruction, bleed, fistula formation, or perforation), liver dysfunction, kidney damage, and radiation enteritis.
- Acute toxicity including Grade 4 nausea, Grade 4 skin toxicity, and Grade 3 liver toxicity will be referred to as dose limiting toxicities (DLT).
- Late toxicity including any Grade 3+ GI toxicity (small bowel damage including stricture or obstruction, bleed, fistula formation, or perforation; liver damage including ascites but not including abnormal lab values only; pancreatitis, cholecystitis) will be considered a toxicity of interest.
- All life-threatening Grade 4 and all fatal toxicities (Grade 5) must be reported immediately and evaluated.

- Acute toxicity: Acute side effects are considered as occurring \leq 28 days from the start of radiation therapy. They will be documented using the NCI Common Terminology Criteria for Adverse Events (CTCAE) version 3.0 (A copy can be downloaded from <http://ctep.info.nih.gov>). The relevant sections are included in the appendix.
- Late toxicity: Late side effects are considered as occurring $>$ 28 days from the start of radiation therapy through a 12 month total evaluation period. They will also be documented using the NCI Common Terminology Criteria for Adverse Events (CTCAE) version 3.0. The relevant sections are included in the appendix.
- University of Chicago Reporting Guidelines
 - If the reaction requires reporting, the Research Nurse or MD reports the adverse reaction to the Cancer Clinical Trials Office (CCTO) at [contact] by the end of the business day when he/she becomes aware of the event. Events occurring after business hours will be reported to the CCTO by 12 pm (noon) the next business day.
 - The following information is required when calling in the event:
 - Caller's Name and Telephone Number
 - Patient Initials
 - Patient Medical Record Number
 - IRB Protocol Number
 - PI of Study
 - Attending Physician
 - Date of Event
 - Description of Event (including grade of the event and attribution of the event and if the event required hospitalization)

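### The DLT window runs from the first fraction in 4.3 and 6 but is described as post-RT in 3.2.2, and the 3-week evaluability rule fits neither

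*Combined protocol and SAP*

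**What the plan says.** Three places in the combined protocol and SAP give the length of the DLT or acute period.

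- Section 4.3, the operative definition: "The evaluation period of acute toxicity will be defined by the period of 28 days following the first fraction of RT".
- Section 6 uses the same anchor. Acute effects are those up to "28 days from the start of radiation therapy", and later ones are late toxicity.
- Exclusion 3.2.2 bars "Concurrent investigational therapy delivered over the period of treatment or observation (28 days post-RT) for dose limiting toxicity".

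The Schema speaks of a 4-week evaluation period without naming its starting point.

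On course length, 5.2.5 says "RT is to be delivered to each site in 3 fractions over a period of up to 10 total days" and 4.5 says "Duration of SBRT is to occur within a 10 day time period". Section 4.5 also lists circumstances introduced by "Completion of the three fractions of RT will be delayed or foregone if", with no stated limit on the delay.

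Section 4.3 adds two further conditions. A patient needs at least 3 weeks of follow-up from RT start to contribute to the DLT assessment, although a DLT seen earlier still counts. The liver DLT requires persistence to day 28. In the study calendar, visits are every 2 weeks in the first month from RT start and then at month 2.

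**The concern.** The DLT count drives every escalation decision and therefore the primary objective, the MTD of three fractions. Two separate matters arise.

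First, 3.2.2 on its face describes a longer DLT observation period than 4.3 and 6 define. A team working from 3.2.2 and a team working from 4.3 could classify the same event differently.

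Second, even if 3.2.2 is set aside, the clock in 4.3 starts when one of three fractions has been given. Observation after the complete treatment then depends on how fast the course was delivered, so patients at one level are not watched equally long after it. The 3-week rule allows less again. If some acute toxicity appears after the window closes, a level looks safer than it is and is cleared more easily.

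**Working it through.** **Inputs.** Window of 28 days from the first fraction (4.3, 6); 28 days post-RT (3.2.2); course of up to 10 days (4.5, 5.2.5); evaluability at 21 days from RT start (4.3). Let L be the days from first to last fraction. For a 10-day course, L = 10 if the 10 days are elapsed days, or 9 if they are counted inclusively.

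**Step 1: closing dates, in days from the first fraction.**
- Sections 4.3 and 6: day 28.
- Section 3.2.2 read literally: 28 + L = 38 (or 37).
- Gap: 10 (or 9) days.

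**Step 2: observation after the last fraction under 4.3.**
- Full window: 28 − L = 18 (or 19) days.
- Minimum for a patient counted as DLT-free: 21 − L = 11 (or 12) days, and fewer if a fraction is delayed past day 10.
- A patient released at day 21 leaves 28 − 21 = 7 days of the window unobserved and cannot be assessed for liver toxicity that must persist to day 28.

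**Step 3: which rule governs an event in the gap.** Grade 3+ enteritis is on both the acute DLT list and the late list in 4.3. If it begins on day 32 after a course with L = 10, it falls 22 days after the last fraction. Under 4.3 and 6 it is late toxicity. The only late-toxicity rule is suspension at 7 or more of the 18 patients at the putative MTD. In a patient treated at a level that does not become the MTD, the event enters no decision rule.

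**Step 4: the plan's own figures.** The plan gives no operating characteristics for escalation. Its only figures concern the cohort of 18:
- P(X ≥ 7 | n = 18, p = 0.50) = 0.881, stated as 0.88.
- P(X ≤ 6 | n = 18, p = 0.25) = 0.861, stated as 0.86.

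Both reproduce, and neither depends on the window.

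**Step 5: size of a possible undercount.** Under the table in 4.3, with exactly three patients added after 1 of 3, a level is cleared with probability

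P(p) = (1 − p)³ + 3p(1 − p)² × (1 − p)³.

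At p = 0.30: 0.343 + 0.441 × 0.343 = 0.494. Let c be the share of DLTs (first fraction to 28 days after the last) that the 4.3 window captures, so the counted rate is c × p.

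| Share captured, c | Counted rate, true 30% | P(clear) | Counted rate, true 40% | P(clear) |
|---|---|---|---|---|
| 100% | 0.300 | 0.494 | 0.400 | 0.309 |
| 90% | 0.270 | 0.557 | 0.360 | 0.378 |
| 80% | 0.240 | 0.622 | 0.320 | 0.454 |
| 64% (18/28) | 0.193 | 0.724 | 0.257 | 0.584 |

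The last row assumes that every course takes 10 days, that onset is uniform over the 28 days after the last fraction, and that no DLT occurs between fractions. Relaxing this at a true 30%:
- Uniform onset from the first fraction to day 38 gives c = 28/38 and P(clear) = 0.66.
- Uniform onset after the last fraction with L = 5 gives c = 23/28 and P(clear) = 0.61.

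The table does not include the further loss from patients counted at 21 days.

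**The case against.** The best defence is that the plan already has one operative window. Sections 4.3 and 6 agree, the calendar visits are counted from RT start, and 9.2 counts late toxicity from RT start too. Section 3.2.2 is an eligibility clause with the period in a parenthesis. Its wording may simply be loose, and read literally it only bars other investigational therapy for longer than the DLT window. This stands. A reader might infer that the primary endpoint has two operative closing dates, or that 3.2.2 makes a day-32 enteritis a DLT. The documents do not support that, because 3.2.2 does not define DLT.

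Three other inferences should also be resisted.
- The short observation after the last fraction is not caused by the conflict. It follows from the first-fraction anchor and the 10-day course, and deleting the parenthesis would leave it unchanged.
- The 18 days is not the minimum, because the 3-week rule allows 11–12.
- A late event at an escalation level is not one of six tolerated events. That tolerance belongs only to the cohort of 18 at the putative MTD.

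There are partial safeguards. Fatal toxicity considered related to RT is a DLT, with no window attached in that sentence. Toxicity is assessed before each fraction after the first, reviewed weekly, and followed to 12 months. These make it unlikely that an event goes unseen. They do not say whether a non-fatal event in the gap counts toward escalation.

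**Conclusion.** The point holds as a question of consistency and definition for the primary endpoint. Section 3.2.2 and sections 4.3 and 6 describe DLT observation periods that end up to 9–10 days apart. Independently, 4.3 leaves 18–19 days of its window after the last fraction of a 10-day course. It accepts as DLT-free a patient with 11–12 days, which fits neither its own 28-day window nor the liver criterion.

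The effect on escalation is directional rather than measured. Any acute DLT that starts after the window closes makes a level easier to clear. At a true rate of 30%, the chance of clearing goes from 0.49 to between 0.56 and 0.72 when 90% down to 64% of events are captured. A reader might take 0.72 as the expected result. It is the most unfavourable of the scenarios worked, and the documents give neither onset times nor actual course lengths. If nearly all acute DLTs begin early or courses are short, the effect is small.

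**What to change.** Reconcile 3.2.2, 4.3, 6 and the Schema so that they state one DLT window with one named anchor.

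- Consider the post-RT wording already in 3.2.2, running from the first fraction to 28 days after the last fraction received. It gives every patient the same observation after treatment, whatever the course length, and it remains defined if a fraction is delayed or omitted. If the first-fraction anchor is kept, correct 3.2.2 and acknowledge the unequal follow-up after the last fraction.
- Start the late period on the next day, so that every event falls under exactly one rule.
- Require a DLT-free patient to complete the window to be evaluable. Reconcile the 3-week rule and the day-28 condition in the liver criterion with it, and keep the provision that an earlier DLT counts.
- Align a calendar visit with the close. A window ending at day 37–38 falls between the month 1 and month 2 visits.

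The cost is an amendment to the wording, up to about 10 extra days before each escalation decision, and one visit moved or added. Patients who do not complete the window may also need replacing for the DLT assessment.
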